### 3 STUDY DESIGN

This will be a four-arm cluster-randomized trial based on an underlying 2x2 factorial design. A random sample of 48 PPMVs (clusters) will be selected from a complete sampling frame of all eligible outlets and subsequently randomly assigned in a 1:1:1:1 ratio to each of the 4 arms (see Table 2).

All clusters (Arm 1-4) will have access to RDTs at the wholesale price that enables the outlet to charge the desired retail price. The study will pre-specify the retail price so that it is consistent across all the arms and pharmacies and will work with in-country wholesalers to provide RDTs at the appropriate price to all participating outlets. In addition, all outlets will be trained on a mobile reporting app and asked to use it to record RDT and ACT sales and to facilitate payment of financial incentives. The four treatment arms are as follows:

- (1) Control (Arm 1): No price subsidy or incentive. RDTs are made available at wholesale price to the retail outlet.
- (2) Provider-directed intervention (Arm 2): Retail outlet in this arm receives a small incentive to perform an RDT for suspected malaria cases
- (3) Client-directed conditional ACT subsidy (Arm 3): Clients visiting outlets in this arm will receive an ACT discount *if* they purchase a malaria test and have a positive test result.
- (4) Combined interventions (Arm 4): Retail outlets in this arm receive an incentive to test for malaria and clients visiting these outlets receive an ACT discount conditional on a malaria positive test (i.e. this arm is a combination of the provider-directed and client-directed interventions that are offered in Arm 2 and Arm 3).

Our four-arm study design will allow us to measure the effect of joint incentives to the provider and consumer, relative to no incentives and relative to either incentive alone.

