Our primary outcome—the proportion of ACTs that are taken by malaria test-positive clients—is a combination of the proportion of individuals who get tested for malaria and the proportion of tested individuals who treat according to the test result. We anticipate that 15% of ACTs will be purchased by clients with a positive test in the control arm (with 85% of ACTs purchased by those without a test or with a negative test). Moreover, we hypothesize that both the provider-directed intervention, and the client directed intervention on their own will only increase testing marginally (on the order of ~5 percentage

points), but that among those who do test, the client-directed intervention alone will substantially increase the proportion of malaria-positive individuals who take an ACT [30]. As a result, we expect that the provider-directed intervention (Arm 2) will have only a small effect on ACT targeting, that the client-directed intervention (Arm 3) will have a somewhat larger effect, but that the largest effect will come from combining the two interventions (Arm 4) (i.e., we assume a statistical interaction). With a sample of 170 exit interviews per outlet (48 outlets in Nigeria), we will have >90% power to detect a minimum difference between Arms 1 and 4 in the primary outcome of 25 percentage points. We will also have >89% power to detect a minimum difference of 16 percentage points for the main secondary comparison of interest (testing uptake).

Due to the nature of the interventions, it is not possible to blind participants and the implementation team to the allocation received. Data collectors will be blinded throughout collection and study statisticians will be blinded during the analysis phase.

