#### Section 4: Purchase Questions

| Number | QUESTION   | RESPONSE   | SKIP  |
|--------|--|--|---|
| 4.1    | Which medicine(s) did you obtain from the shop today to treat your/your child's illness
Choose all that apply   | 1. AL (Lonart/CoArtem/Artefan)
2. Other ACT (DHAP, DP, Duocotexin, P-alaxin)
3. Other antimalarial (Artesunate injection, Quinine, Chloroquine, SP/Fansidar)
4. Antibiotic (Amoxyl/Ceprin, Metronidazole/Flagyl, Ampicillin)
5. Painkiller/fever medicine (Panadol/Brufen/Hedex/ Action)
6. Cough medicine or decongestant
7. Other _____
8. None
99. Don't know | If 2, 3, 4, 5, 6, 7 or 99
Skip to 4.4

If 8, skip to 5.1 |
| 4.2    | How much did you pay today for the ACT?

(The amount refers to how much money respondent paid for the ACT. Don't add the amount of the voucher if any was used-the amount should be between 0-5000, or 9999 for don't know) | ACT= _____ Naira

OR

Don't know/remember...9999   |   |
| 4.3    | How much did you spend at the chemist/shop today? (Total cost to client including RDT, ACT and any other drugs)   | _____ Naira  |   |
| 4.4    | Was there any discount for your ACT at the shop today?  | 1. Yes
2. No
3. Don't know   |   |

|     |   |   |   |
|-----|---|---|---|
|     |   |   |   |
| 4.5 | I would like to record information about each drug you purchased today. May I see the packaging? | 1. Type _____
2. Brand Name _____
3. Price _____ Naira
4. Did participant show you the drug?
1. Yes
2. No | Repeat for every drug purchased for illness |

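### Data collectors cannot stay blinded throughout to the client-subsidy factor, because their own exit form collects the ACT discount and price, and the study discount exists only in Arms 3 and 4

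*Combined protocol and SAP*

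**What the plan says.** The last paragraph of Section 6.2 (Sample Size Considerations) says that "it is not possible to blind participants and the implementation team to the allocation received". It then says of the interviewers: "Data collectors will be blinded throughout collection". Statisticians are to be blinded during analysis. Nothing says how collectors are kept blind. Section 3 assigns collectors to outlets at random, but the reason given is to limit changes in behaviour caused by an interviewer's presence.

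Section 3 defines the arms. Arm 1 has "No price subsidy or incentive". In Arm 2, "Retail outlet in this arm receives a small incentive to perform an RDT for suspected malaria cases". Only Arms 3 and 4 give the client an ACT discount, and only after a positive test at the outlet.

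In the appended exit interview, Section 4 (Purchase Questions):

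- Item 4.4 asks: "Was there any discount for your ACT at the shop today"?
- The skip rule at item 4.1 sends codes "If 2, 3, 4, 5, 6, 7 or 99" straight to 4.4. Buyers of artemether-lumefantrine (AL, code 1) reach it through 4.2 and 4.3. Only clients who obtained nothing go past it.
- Item 4.2 records what was paid for the ACT, with the interviewer note "Don't add the amount of the voucher if any was used".
- Item 4.5 records the price of each drug obtained.

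**The concern.** The same people are declared blind to allocation and told to collect information that can disclose half of it. When a client who tested positive at the outlet reports a discount or shows a reduced ACT price, the collector has good reason to place that outlet in Arm 3 or 4. Within that interview, the test items (3.1, 3.3) and the medicine item (4.1) have already been answered. The risk lies in later interviews at the same outlet.

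The exposed tasks are approaching clients, judging eligibility, recording the self-reported shop test result and, at item 2.9, coding an outside positive as seen on a report or only reported by the respondent. The last matters because Section 6.1 counts an outside positive in the primary numerator only if it is documented. Since clients and implementers are open, collector blinding is the main stated safeguard at data capture. If the statement stands, the trial will report a blinding of outcome assessment that its own form does not support for this factor.

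**Working it through.** The plan gives no figure for blinding, so there is none to reproduce. The check has two parts.

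**1. Who is asked, and what an answer reveals**

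| Item 4.1 response | Route | Reaches 4.4? |
|---|---|---|
| AL (1) | 4.2, 4.3, 4.4 | Yes |
| Other ACT, other drugs, don't know (2–7, 99) | skip to 4.4 | Yes |
| None (8) | skip to 5.1 | No |

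| Comparison (Section 6.2) | Do the arms differ in the client discount? | Can the form reveal the difference? |
|---|---|---|
| Arm 4 v Arm 1 (primary) | Yes | Yes |
| Arm 4 v Arm 2 | Yes | Yes |
| Arm 4 v Arm 3 | No, only in the provider incentive | No; no item asks about it |

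**2. How often a discounted purchase would be met**

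Inputs:
- p, the share of ACTs taken by test-positive clients: 26% (Arm 3) and 40% (Arm 4), from Table 2.
- Interviews: a target of 10 per outlet per month (Section 3) and 170 per outlet (Section 6.2).
- a, the share of interviewees who buy an ACT: **assumed** 10% to 80%. Section 6.3 says only that a subset do.
- e, the share of test-positive ACT buyers who were tested at the outlet and used the discount: **assumed** 50% to 100%. Table 2 includes referred positives, who cannot receive it (Section 3), so e may be below 100%.

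With interviews treated as independent:
- Chance per interview: q = a × p × e
- Chance of at least one in n interviews: 1 − (1 − q)^n

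Low end (a = 0.10, e = 0.5):
- Arm 3: q = 0.10 × 0.26 × 0.5 = 0.013. In 10 interviews, 1 − 0.987^10 = 12%. In 170, 1 − 0.987^170 = 89%.
- Arm 4: q = 0.10 × 0.40 × 0.5 = 0.020. In 10 interviews, 1 − 0.98^10 = 18%. In 170, 1 − 0.98^170 = 97%.

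High end (a = 0.80, e = 1):
- Arm 3: q = 0.208. In 10 interviews, 1 − 0.792^10 = 90%.
- Arm 4: q = 0.320. In 10 interviews, 1 − 0.68^10 = 98%.
- In 170 interviews, both are effectively 100%.

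| a | e | Arm 3, 10 interviews | Arm 4, 10 interviews | Arm 3, 170 | Arm 4, 170 |
|---|---|---|---|---|---|
| 10% | 50% | 12% | 18% | 89% | 97% |
| 20% | 50% | 23% | 34% | 99% | >99% |
| 20% | 100% | 41% | 57% | >99% | >99% |
| 80% | 50% | 67% | 83% | >99% | >99% |
| 80% | 100% | 90% | 98% | >99% | >99% |

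These chances are per outlet, pooled over whoever collects there. They describe exposure to revealing information, not bias in the outcome.

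**The case against.** **The form is the same in every arm, and a question alone unblinds no one.** This stands. Only the answer can inform. A no tells little about most clients, and a shop's own discount could produce a yes. But a yes from a client who tested positive at the shop, or a reduced ACT price at item 4.2 or 4.5, is strong evidence of a subsidy arm.

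**A reader might infer that collectors ask every buyer about a voucher tied to Arms 3 and 4.** The documents do not support that. The word occurs once, as a recording note in item 4.2. That item is reached through the AL code, and no section links a voucher to an arm. The point rests on item 4.4 and the prices.

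**A reader might infer that the blinding does not exist at all.** That is too strong. No item touches the provider incentive, so the form leaves Arm 4 v Arm 3 and Arm 2 v Arm 1 masked. Not telling collectors the allocation would still be worthwhile.

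**Random assignment of collectors may break carry-over.** In part. It could slow the build-up of one collector's knowledge about one outlet. The number of collectors and the frequency of reassignment are not stated, so per-collector exposure cannot be calculated. Section 3 does not offer the assignment as a blinding measure, and collectors may share what they learn.

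**The route to bias is narrow.** Largely fair. Section 4.1 makes all clients attending on a selected day eligible for screening, shop results are self-reported, and the code for an observed report is factual and is followed by item 2.10. Still, no section requires consecutive approach, and none of this makes the blinding statement true.

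**Conclusion.** The statement in Section 6.2 is wrong as written. Blinding of collectors cannot be maintained throughout collection for the client-subsidy factor (Arms 3/4 v 1/2), and that factor is part of the primary comparison. The finding on the form's routing and the arm definitions needs no assumption. The size of the exposure rests on the Table 2 percentages, the assumed ranges for ACT purchase and discount use, and independence between interviews.

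Two further readings should be resisted. One is that unmasking would come at a known early date, such as within two months. That needs a count of ACT buyers per outlet, which the plan does not give. About 33 can be backed out of the 89% power in Table 2, using its 26% v 40%, 12 outlets per arm, ICC 0.006 and alpha 1.667%. It would be 33/170 = 19% of interviewees, inside the range used above, but it is an inference. The other is that the results are biased. Nothing in the documents shows or sizes a bias; the defect lies in what the trial can claim about its outcome assessment.

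**What to change.** 1. **Replace the sentence in Section 6.2** with wording such as: *Data collectors are not told the allocation, but answers on discount and price can reveal the client-subsidy arms, so outcome assessment is not considered blinded for that factor.* If collectors are rotated between outlets, state how.
2. **Keep item 4.4 and the price items, after the test and medicine items.** Deleting 4.4 would not restore masking, because items 4.2 and 4.5 still show a reduced price. It would also remove a client-reported check that the subsidy was delivered. Section 3 regards exit interviews as more reliable than provider reports.
3. **Make selection checkable.** Approach exiting clients consecutively on interview days. Record Outlet ID on the screening page: at present it is item 0.3, after the form has stopped for anyone excluded or refusing. Keep a tally of clients approached, since under Section 8 a client who declines at first contact is never screened. Compare approached, eligible and refused counts by arm.

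The cost is a small form edit, a short tally on each interview day, and a less favourable blinding statement in the report.

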### 6.3 Participant Enrollment and Follow-Up

Medicine retail outlets will be eligible if they regularly stock and sell regulatory approved ACTs and are licensed medicine outlets. From this roster of all eligible outlets, 56 will be randomly selected (8 additional above the required sample size). Of those retail outlets, 48 outlets will be randomly selected for training and enrollment in the study and will be randomized to one of the 4 study arms in a 1:1:1:1 ratio. The remaining 8 outlets will be alternates in the event that any of the initial outlets drop out of the intervention. The alternate outlets will also be

randomized equally across the 4 study arms (2 alternates per arm per site), but they will not undergo training unless they are needed for replacement.

We will retain these enrolled outlets through effective supportive supervision and communication between providers at participating outlets and study staff. All outlets will receive thorough, in-person training on using the mobile reporting tool, conducting RDTs and overall study procedures. They will also receive extra support during the start of the intervention and burn in period (3 months), including an initial stock of RDTs provided by the study at no cost. At least once per month, the Project Manager, and/or Field Coordinator will visit each outlet in person to answer questions, check RDT stock and testing performance, and identify and address any problems. Providers will also receive phone calls from the Field Coordinator and Project Manager between in-person visits and will themselves be provided with phone numbers and encouraged to call the study staff with any questions or concerns. Additionally, outlets will be reimbursed promptly to ensure participation in the study presents no financial strain.

In our previous work, we have experience on the retention of outlets in research activities and therefore expect attrition of clusters. Should one of the outlets selected choose to leave the study within the first 6 months of the intervention, the outlet will be replaced by one of the alternate outlets assigned to the same arm. If any outlet chooses to leave the study after the first 6 months of the intervention, they will not be replaced because, after joining the intervention at such a late stage, a newly added outlet is not likely to be comparable to that of all other participating outlets. Changes in the clusters (dropped and/or replaced) will be accounted for in the analysis.

Our sample size estimates correspond to a total of 8160 exit interviews with clients. Since not everyone interviewed will have purchased an ACT, our estimates account for the fact that only a subset will enter into our analysis for the primary outcome.

## 6.4 Analysis Plan

We will analyze client-level outcomes by fitting a modified Poisson regression model [31, 32] with log link to estimate risk ratios (RRs) and identity link to estimate risk differences. Such an approach assumes a Poisson distribution for the binary outcome and then 'fixes' the estimated standard errors to correct for model misspecification.

To account for clustering by outlet we will use a generalized estimating equations (GEE) [33, 34] approach with exchangeable working covariance matrix and robust standard errors (to correct for model misspecification due to specifying a Poisson distribution). The outcome will be regressed on three binary indicators for each of the treatment arms 1-3, with treatment arm 4 (the combined interventions) serving as the reference group. The model will also include a vector of potential confounder variables (e.g., age, gender, education, household distance to closest health facility, study quarter) to account for possible imbalances between study arms. All analyses will be based on the intention-to-treat principle whereby all clients will be included in the analysis irrespective of whether they complied with the intervention in the outlet at which they sought care (e.g. even if they did not use the ACT subsidy if they tested positive in an outlet in Arms 3 and 4 that received the client-directed intervention).

Given that the literature indicates that when there are fewer than 40 clusters in a cRCT, small sample correction methods should be used to ensure that standard error estimates are correctly estimated when using GEE to analyze binary outcomes, and given that the size of the cRCTs in each country are close to this cut-off, we plan to adopt the use of the Kauerman-Carroll correction to avoid any possible problems [35, 36]. We will compare secondary outcomes using the same modeling approach.

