## 6.2 Sample Size Considerations

Our primary comparison of interest is the effect on targeting of ACTs, offering a combination of outlet incentives for testing (provider-directed intervention), and ACT subsidies for malaria test-positive clients (client-directed intervention) relative to a control arm where outlets are able to offer malaria testing but neither the provider nor the client receives any extrinsic incentive to test (Arm 4 versus Arm 1). In order to evaluate whether the client-directed intervention and the provider-directed intervention do, in fact, have a synergistic effect on the outcome, we also have two secondary comparisons of interest: (1) the combined provider- and client-directed interventions relative to the provider-directed intervention alone (Arm 4 versus Arm 2) and (2) the combined provider- and client- directed interventions relative to the client-directed intervention alone (Arm 4 versus Arm 3).

We calculated power based on a cluster randomized two-sample two-tailed t-test for the comparison of two proportions using standard formulae [28]. We calculated power for differences in our primary outcome for each of the three comparisons of interest noted above. To ensure that our overall two-tailed Type I error (alpha) is 5%, we fixed the alpha level at 1.667% (i.e. 5%/3) for each of the 3 comparisons of interest, using the conservative Bonferroni correction [29]. We estimated the intra-class correlation coefficients (ICCs) for the primary outcome to be 0.006 in Nigeria.

**Table 2:** Assumptions in Nigeria for sample size calculation for Aim 2

|   | Expected Percentage of ACTs taken by Clients Testing Positive for Malaria | Power (# of exit interviews per arm) | Nigeria (2040) |
|---|---|--------------------------------------|----------------|
| Arm 1: Control Arm
(RDT only, no incentives)  | 15%   | >99%                                 |                |
| Arm 2: Provider-Directed Intervention (Shopkeeper incentives for malaria testing)        | 17%   | >99%                                 |                |
| Arm 3: Client-Directed Intervention (ACT subsidy to client conditional on positive test) | 26%   | 89%                                  |                |
| Arm 4: Combined Provider- and Client-Directed Interventions                              | 40%   | Ref. Group                           |                |

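### Section 6.4 gives a small-sample standard error but no reference distribution or degrees of freedom, so the promised 5% overall error is not secured on contrasts of 12 v 12 outlets

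*Combined protocol and SAP*

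**What the plan says.** Section 6.2 sets out to hold the overall two-sided type I error at 5% over three contrasts, each against Arm 4: "we fixed the alpha level at 1.667% (i.e. 5%/3) for each of the 3 comparisons of interest, using the conservative Bonferroni correction". The power calculation there uses a "cluster randomized two-sample two-tailed t-test for the comparison of two proportions".

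Section 6.4 analyses the data differently, with a modified Poisson GEE, an exchangeable working covariance, robust standard errors and three arm indicators with Arm 4 as reference. Its case for a small-sample measure is that "when there are fewer than 40 clusters in a cRCT, small sample correction methods should be used", and that this trial is close to that number. It concludes: "we plan to adopt the use of the Kauerman-Carroll correction to avoid any possible problems". The stated aim is correct standard errors. No reference distribution or degrees of freedom is given for any GEE test or interval. Secondary outcomes are to be analysed in the same way.

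On the number of clusters, section 6.3 says that "48 outlets will be randomly selected for training and enrollment in the study and will be randomized to one of the 4 study arms" in equal ratio, which is 12 per arm.

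**The concern.** Few clusters cause two separate problems for a GEE Wald test. The sandwich variance is biased downwards, and it is itself imprecise. The Kauermann-Carroll correction deals with the first. The second is normally handled by a t reference on the between-cluster degrees of freedom, and section 6.4 is silent on that while presenting the correction as enough.

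The plan also judges its cluster count by the trial total of 48. That total is not what each test rests on: a contrast of one arm with Arm 4 draws its treatment information from 24 outlets, well under the plan's own cut-off of 40.

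At stake is the 5% overall error that section 6.2 undertakes to ensure, and the width of every reported interval. Two analysts could both follow section 6.4 to the letter and use different critical values, only some of which keep that undertaking.

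**Working it through.** **Inputs from the documents.** Overall alpha 5%, three comparisons, 48 outlets in four equal arms, ICC 0.006, expected proportions 15%, 17%, 26% and 40% in Arms 1 to 4, 170 interviews per outlet, stated power 89% for Arm 4 v Arm 3.

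**Assumed, because the documents do not give them.** The reference distribution of the GEE tests, the number of ACT buyers per outlet and its coefficient of variation (CV), and the covariate structure.

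1. *The plan's own figures.* 0.05/3 = 0.01667, as stated. 48 x 170 = 8160 and 12 x 170 = 2040, as stated.

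2. *Critical values at two-sided alpha 0.01667.* Normal: 2.394. t on 44 df (48 outlets minus 4 arm parameters): 2.489. t on 22 df (24 outlets minus 2): 2.591.

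3. *Error per contrast, equal outlet sizes, arms only in the model.* Here the correction multiplies each arm's sandwich variance by 12/11, which makes it unbiased, and the Wald statistic behaves approximately as t on 22 df.
   - Normal reference: P(|t22| > 2.394) = 2.56%.
   - t on 44 df: P(|t22| > 2.489) = 2.1%.
   - t on 22 df: 1.67%.
   - Normal reference with one outlet lost per arm (20 df): P(|t20| > 2.394) = 2.66%.

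4. *Family-wise error under the global null.* From 2,000,000 simulated trials with four arms of 12 outlets and Arm 4 shared by all three contrasts:

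| Reference | Per contrast | Family-wise |
|---|---|---|
| Normal | 2.6% | 6.7% |
| t, 44 df | 2.1% | 5.5% |
| t, 22 df | 1.67% | 4.5% |
| Normal, variances known | 1.67% | 4.5% |

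   The last row shows the slack left by Bonferroni with a shared arm: about half a point, too little to absorb the excess.

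5. *Check with fitted GEE models.* These used clustered binary data, an exchangeable working correlation, the Kauermann-Carroll variance and a normal reference. The runs with covariates had 6,000 trials per setting, so Monte Carlo error is about 0.1-0.2 points per contrast and 0.3-0.4 points family-wise.
   - Equal sizes: about 2.3-2.6% per contrast and 6.3-6.9% family-wise.
   - Assumed size CV 0.5, with and without covariates: roughly 2.6-3.1% and 6.8-7.8%.
   - Assumed size CV 0.8, no covariates: 3.6% and 9.1%.
   - With t on 22 df instead: family-wise 4.5% at equal sizes, up to 5.4% at CV 0.5, and 6.6% at CV 0.8.

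6. *Does the stated power show which reference was meant?* For 40% v 26% with m ACT buyers per outlet, SE = sqrt[(0.40 x 0.60 + 0.26 x 0.74)/m x (1 + (m - 1) x 0.006)/12].
   - m = 33: SE = 0.0361 and 0.14/SE = 3.88. Power is 89.0% with t on 22 df.
   - m = 28: SE = 0.0387 and 0.14/SE = 3.62. Power is 89.0% with z but 83.8% with t on 22 df.

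   The number of buyers is not stated, so 89% fits either basis.

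7. *Would the primary contrast change?* For 40% v 15% at m = 33, SE = 0.0333 and 0.25/SE = 7.5. Moving the critical value from 2.394 to 2.591 makes no difference there.

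**The case against.** The strongest reply is that the plan never says z. The only test distribution it names is the t-test in section 6.2, and a team that carries this into the analysis with 22 df largely removes the inflation. This stands, and it rules out the tempting reading that the plan prescribes a normal test and therefore breaks its 5% commitment. But the t-test in 6.2 is described for the power calculation only, and nothing carries it into 6.4. The two references cited for the correction do not fill the gap, because section 9 lists them as publications on a malaria medicines subsidy facility.

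It can also be said that 48 exceeds the cut-off of 40 and the plan corrects anyway, so counting 24 outlets would lead to the same correction. True for the standard error. It is not true for the degrees of freedom: 44 and 22 give different critical values, and 44 does not hold 5%.

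The upper figures depend on an assumed CV of ACT-buyer counts. Section 3 sets interview days by sales volume with a common monthly target per outlet, which should even out interview counts, although the share buying an ACT may still differ between outlets. The equal-size figures are therefore the firmer ones.

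Finally, the effect is modest. Even with z, the one contrast that section 6.2 calls primary runs well below 5%, and the family-wise figures hold only under the global null. All of this stands and limits how far the point reaches.

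**Conclusion.** The gap is real and of moderate size. Section 6.4 names a standard-error correction as its whole small-sample remedy and leaves the reference distribution and degrees of freedom open. Under a normal reference, which is an assumption, the error is about 2.6% per comparison and 6.7% family-wise with equal outlet sizes, against 1.667% and 5%. With an assumed size CV of 0.5 it is roughly 2.6-3.1% and 6.8-7.8%. With t on 44 df it is about 5.5% family-wise.

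A reader might infer that the main conclusion is at risk. The documents do not support that: the planned Arm 4 v Arm 1 difference lies about 7.5 standard errors from zero at 33 buyers per outlet. The exposure is in borderline contrasts, effects smaller than planned, and interval width, including for the secondary outcomes. A reader might equally infer that the stated power is unaffected because it was described as t-based. That cannot be confirmed either, since 89% is also reached with z at 28 buyers per outlet.

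**What to change.** Add to section 6.4 that each pairwise contrast is tested, and its interval built, with the Kauermann-Carroll standard error and a t distribution with df equal to the number of outlets contributing to the two arms minus 2. That is 22 df and a critical value of 2.591 if all outlets are retained, and fewer df if outlets leave without replacement. This matches the t-test basis of section 6.2.

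The cost is one sentence and intervals about 8% wider than with z (2.591/2.394 = 1.08). If ACT-buyer counts prove very uneven, t on 22 df remains somewhat liberal (6.6% family-wise at CV 0.8), and a randomisation test would be a reasonable sensitivity analysis.

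Section 6.2 should also state the assumed number of ACT buyers per outlet and confirm that the 89% was computed with this t reference. If it was z-based, the figure should be restated; it would be about 84%.
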